# 26 APPENDIX 3: DAILY DIARY

Note: The diary includes bleeding definitions to ensure consistent assessment of bleeding amongst study subjects. However, the definitions are based upon the use of tampons or pads. Subjects using menstrual cups should be instructed to use their best judgment to assess their level of bleeding each day since the bleeding definitions within the diary will not apply.

CCN016 IUD Daily Diary	Start Date of 28 Day		Version 01.00 2017 0509
Subject Number:	interval:	MMM-DD-YYYY	

B	Date	MMM-DD	MMM-DD	MMM-DD	MMM-DD	MMM-DD	MMM-DD	MMM-DD	MMM-DD	MMM-DD	MMM-DD	MMM-DD	MMM-DD	MMM-DD	MMM-DD
ı	None				0	-				-				0	
e e	Spotting			0	-	0			-	-		0	0	-	
d	Light bleeding			0									0		
i	Moderate bleeding		п												
n	Heavy bleeding	 			0			0	-			0		0	
g	Diary Day	1	2	3	4	5	6	7	8	9	10	11	12	13	14

В	Date	MMM-DD													
ī	None			D						0		10	D		
e e	Spotting		-	-						-			-	-	
d	Light bleeding	0		0						0	0	0	0	0	
i	Moderate bleeding	0	0	0	0	-		0	0	0		0	0	0	-
n	Heavy bleeding			В	_			0		0		0	В	_	
g	Diary Day	15	16	17	18	19	20	21	22	23	24	25	26	27	28

	No	Yes
Did you have vaginal intercourse in this 28 day interval?		
60 - 86	No	Yes
Did you use any other contraceptive method in this 28 day interval?		
	Condom	Other
If any other contraceptive method was used, what method was used?		

Dates will be prepopulated for you by the study staff.

Complete bleeding information every day between your study visits. Provide responses on intercourse, contraceptive method and pain experienced for each full interval prior to finishing each diary form. Remember to bring the completed diary form back to your next visit. If you have any questions on how to complete the form, please ask the clinic staff.

Did you have any pelvic pain during this 28 day interval?	No	Yes					
If yes, was this pain during your period, outside of your period, or both during and outside your period, or both during and outside your period.	period?		During period	Outside of	period	Both during and of period	outside

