3.2. Secondary Endpoints

- IUD continuation throughout 37 months of the study duration
- Failed IUD insertion, uterine perforation, or IUD expulsion (complete and partial)
- Vaginal bleeding patterns
- Pelvic pain and dysmenorrhea
- Other adverse effects
- Pain with and shortly after insertion
- Ease of IUD insertion
- Overall product satisfaction

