7.5.2 Statistical methods

The descriptive statistics of per-subject mean and median number of evaluable cycles and the proportion of evaluable cycles that include any heavy bleeding, a prolonged bleeding episode (e.g., greater than 14 days), amenorrhea (absence of all bleeding and spotting), or bleeding in more than 1/3 of days in the evaluable cycle will be tabulated. In addition, descriptive statistics of bleeding diary data as described by Mishell, et al (2007) such as the mean, median, and range of the total number of heavy, moderate, light bleeding, or spotting days per evaluable cycle will be reported without considering the feature of repeated cycles from same study participants.

To incorporate the nature of repeated measures and partial evaluable cycles, a multinomial regression with generalized estimating equation (GEE) approach will be used to estimate and compare the mean, and total number of heavy, moderate, light bleeding, or spotting days per 28-day cycle equivalent between treatment groups (Liang and Zeger, 1986, and Lipsitz et al., 1994).

Note that if 1) there are sizeable participants discontinued early (e.g., 20% of IUD removal) due to increased menstrual blood loss or due to intermenstrual bleeding/spotting, and 2) the proportions of these two reasons of discontinuation are notably different between treatment groups (P-value < 0.1), the analyses of observed bleeding diary data are likely to be biased due to informative censoring and attrition (Hubacher et al., 2009). In this event, subgroup supporting analyses based on participants' discontinuation reasons related and non-related to blood loss/bleeding/spotting will be conducted. A stratified bleeding diary supporting analysis based on the same blood loss/bleeding/spotting related reasons will also be performed to compare the results from the above analyses. The findings of these supportive analyses will be interpreted cautiously.

For the analysis of pelvic pain data, the proportions of participants experiencing any pelvic pain during 28-day cycle, pelvic pain during period, outside of period, and both during and outside of period will be calculated using binomial distribution for each group, and compared between groups using chi-square tests. In addition, generalized linear models with GEE for repeated pelvic pain outcomes will be used to further explore the differences in frequencies of pelvic pain between study groups.

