7.6.7 Characteristics of last menstrual period and product satisfaction

Acceptability data from the User Population on the last menstrual cycle and product satisfaction overall are derived from subject bleeding and satisfaction questionnaires and participant interviews conducted during the six clinic visits and during the three phone calls over the study period.

Data on bleeding and pelvic pain include number of days of bleeding, volume of blood loss (light, medium, heavy), acceptability of blood loss, level of cramping, and intermenstrual bleeding/spotting/cramping. Summaries will be described in contingency tables and displayed graphically in bar charts, by study visit and overall. Chi-squared tests for binary and ordinal outcome data (e.g., light, moderate, heavy blood loss) will be used to compare treatment groups at each visit/phone call. Generalized linear models with GEE will be used to compare the two treatment groups on these measures over time.

As noted in the previous section, if evidence of informative censoring exists due to participants' discontinuation reasons related to bleeding or pain, similar subgroup and stratified supporting analyses will be used to evaluate the impact of censoring mechanism on the results of the bleeding and pain safety data analysis.

Product satisfaction includes three measures: level of satisfaction with the study IUD, whether the participant would recommend the study IUD to others, and how the product compared to expectations. Each measure will be summarized in frequency and percentage by visit and site. A generalized linear model will be used to evaluate the time trend of product satisfaction between groups and to compare the means of changes of satisfaction between groups across all post insertion time points.

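### SAP 7.5.2 lists diary pelvic pain as during, outside and both, but never defines dysmenorrhea as during-or-both or says whether during includes both

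*SAP*

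**What the plan says.** The daily diary (Protocol Appendix 3) first asks, for each 28-day interval, "Did you have any pelvic pain during this 28 day interval". A woman who answers yes is then asked one timing question: "If yes, was this pain during your period, outside of your period, or both during and outside your period". *Both* is an answer of its own, next to *during* and *outside*.

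SAP 7.5.2 turns this into four outcomes. It starts with "the proportions of participants experiencing any pelvic pain during 28-day cycle" and continues with "pelvic pain during period, outside of period, and both during and outside of period will be calculated using binomial distribution for each group". Each is to be "compared between groups using chi-square tests". It adds that "generalized linear models with GEE for repeated pelvic pain outcomes will be used to further explore the differences in frequencies of pelvic pain", without giving the coding of the outcome.

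SAP 3.2 names "Pelvic pain and dysmenorrhea" as a secondary endpoint. The SAP gives no operational definition of dysmenorrhea. SAP 7.5.2 also gives no rule for combining a woman's several cycles into one participant-level result, although the proportions are of participants.

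Menstrual pain appears in two other places. SAP 7.6.7 (last menstrual period and product satisfaction) analyses questionnaire data that include "acceptability of blood loss, level of cramping, and intermenstrual bleeding/spotting/cramping". SAP 7.4 analyses discontinuation, with menstrual pain as one of the reasons.

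**The concern.** Dysmenorrhea is pain during menses, whether or not there is also pain at other times. In terms of the diary it is the *during* box plus the *both* box. No diary analysis in the SAP forms that sum. A programmer who follows 7.5.2 with the raw variable would most naturally test each box alone.

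Coded that way, *during* misbehaves as an outcome. Take two women with the same period pain. One has no other pain and is counted. The other also has pain between periods, answers *both*, and is not counted. A woman who keeps her period pain and develops intermenstrual pain leaves the category, so the score improves as she gets worse. Pain outside the period has the same problem.

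What is at stake is one between-arm contrast on a secondary endpoint, in a trial whose rationale (Protocol section 1) is that a smaller device may cause fewer side effects. If *both* answers occur, that contrast may not measure what its label suggests.

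**Working it through.** The documents give no expected rate, sample size or power for this comparison, so there is no planned figure to reproduce. The calculation below shows how the coding behaves; it does not predict the result.

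**Inputs**
- Women per arm: 880 Mini and 220 ParaGard (Protocol 4.1). SAP section 1 still has 800 and 200.
- Test: two-sided 0.05 with no multiplicity adjustment (Protocol 19.2.2, SAP section 6).
- Women with period pain (during-or-both): 35% on ParaGard. This borrows the figure for painful menses in Protocol 21.3.1, which is not a per-cycle diary rate and has no split by timing. The Mini rate of 25% is assumed.
- Share *s* of women with period pain who answer *both*: not in the documents, so it is varied.
- Simplification: each woman contributes one box, in effect one cycle.

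**Formulas**
- Box-by-box *during* proportion = p × (1 − s).
- Scored difference, ParaGard minus Mini = p_C(1 − s_C) − p_T(1 − s_T). A positive value favours the Mini.
- Power of the pooled two-proportion z test (equivalent to the uncorrected chi-square), main term: Φ[(|d| − 1.96·SE0)/SE1], where SE0 is the pooled and SE1 the unpooled standard error. The opposite tail is added; it matters only when d is near zero.

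**Inclusive coding.** Pooled proportion = (880 × 0.25 + 220 × 0.35)/1100 = 0.27. SE0 = √[0.27 × 0.73 × (1/880 + 1/220)] = 0.03347. SE1 = √[0.25 × 0.75/880 + 0.35 × 0.65/220] = 0.03532. (0.10 − 1.96 × 0.03347)/0.03532 = 0.974, so power is 0.835, or 84%.

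**Box-by-box coding, true difference 10 points**

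| *Both* share, Mini / ParaGard | *During*, Mini | *During*, ParaGard | Scored difference | Power |
|---|---|---|---|---|
| 0% / 0% | 25.0% | 35.0% | 10 | 84% |
| 20% / 20% | 20.0% | 28.0% | 8 | 72% |
| 30% / 30% | 17.5% | 24.5% | 7 | 65% |
| 50% / 50% | 12.5% | 17.5% | 5 | 49% |
| 20% / 25% | 20.0% | 26.25% | 6.25 | 53% |
| 20% / 40% | 20.0% | 21.0% | 1 | about 6.5% |
| 40% / 20% | 15.0% | 28.0% | 13 | 99% |

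**Reversal.** With true rates of 30% Mini and 35% ParaGard and shares of 20% and 40%, the scored proportions are 0.30 × 0.80 = 24% and 0.35 × 0.60 = 21%. A 5-point benefit is scored as 3 points of harm.

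**No true difference.** With 35% in both arms and the same shares, the scored proportions are 28% and 21%, and the test rejects 56% of the time (52% at 800 vs 200).

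**A second set of assumed rates.** With true rates of 50% Mini and 60% ParaGard, an equal 30% share shrinks 10 points to 0.42 − 0.35 = 7 points. Shares of 10% Mini and 30% ParaGard give 0.42 − 0.45 = −3 points, again a reversal.

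**Cycle rule.** The diary covers 12 months. Suppose a participant counts if she ever ticks the box, and suppose independent cycles with *during* ticked alone in 40% of Mini and 35% of ParaGard cycles. Over 13 cycles the proportions are 1 − 0.60^13 = 99.9% and 1 − 0.65^13 = 99.6%, so the contrast nearly vanishes. Independence is an extreme assumption, but it shows that the missing aggregation rule matters as well as the coding.

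**The case against.** A reader might infer that the SAP lays down a scoring rule under which a woman who answers *both* is not counted under *during*. It does not. SAP 7.5.2 is silent, and its list already overlaps, because any pain contains the other three; *both* could therefore be meant as the intersection. Where the SAP wants exclusive categories it says so, as it does for menstrual hygiene products in 7.6.3. This objection stands: the fault is an undefined outcome whose most direct reading is box by box, not a written exclusion.

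A reader might also infer that the coding works against the Mini. The documents do not support a direction. Nothing in them shows that *both* shares differ by arm, and if the larger share is on the Mini, its benefit is exaggerated.

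Nor is the whole dysmenorrhea comparison at risk. Last-period cramping is analysed separately, at visits and calls through the study, with its own tests and GEE models. Discontinuation for menstrual pain is also compared, and any pelvic pain does not depend on the coding. Protocol 19.2.2 places its pelvic pain summaries on the visit forms and uses the diary for bleeding.

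Finally, for a single cycle the reported proportions allow during-or-both to be rebuilt by addition. That is true, but no test of the sum is planned. Across cycles a woman may tick different boxes, so participant-level proportions cannot simply be added.

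**Conclusion.** The point holds as a gap in definition. The diary offers three alternative answers, SAP 7.5.2 repeats them as separate tested outcomes, and no planned diary test is defined to cover all women with period pain.

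If the boxes are analysed one by one, the *during* contrast is diluted when the *both* share is equal and above zero. When the shares differ it can be diluted further, reversed or exaggerated. Under the assumptions above, a 10-point difference is scored as 8 to 5 points with equal shares of 20% to 50%, and as anything from 1 to 13 points with shares of 20% and 40% in one order or the other. If nobody answers *both*, nothing changes.

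These sizes rest on an assumed Mini rate, assumed *both* shares, a ParaGard rate that is not a diary rate, and one box per woman. They illustrate the mechanism only. The primary pregnancy analysis is untouched, and so are the other pain analyses named above. The point is still worth settling before analysis, because otherwise the coding of a named secondary endpoint is left to be chosen once the data are in hand.

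**What to change.** In SAP 7.5.2:

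- Define two overlapping binary outcomes per cycle: dysmenorrhea = *during* or *both*; intermenstrual pelvic pain = *outside* or *both*.
- Use these two, with any pelvic pain, in the chi-square tests and in the GEE models, with the same coding in each.
- State how a woman's cycles are combined for the participant-level proportions.
- Keep the distribution over the three boxes as a descriptive table without tests.

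The cost is a few sentences of SAP text and a recode of an existing diary variable. No new data are needed.

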7.6. Analysis of Other Secondary Endpoints and Safety Data

The ITT population will be used for analyses involving pre-IUD insertion events, and the Treated Population will be used for the safety and other secondary endpoints analyses during the insertion process, and the User Population will be used for the safety and other secondary endpoints analyses after a successful IUD insertion. Descriptive statistics will be calculated by pooling data across

sites. In addition, a supporting analysis will be performed using the Per Protocol Populations if more than 5% of participants in the User Population are excluded.

7.6.1 Exiting the trial before attempting IUD insertion

The ITT Population will be used for estimating the incidence of exiting the trial before attempting an IUD insertion. Reasons for exiting the trial before attempting IUD insertion include:

- Could not sound the uterus
- Shallow uterine depth (less than 5.5cm)
- Medical contraindication discovered post-randomization but before IUD insertion attempt

The frequency and the percentage of women who exited the trial for different reasons before IUD insertion will be tabulated by treatment group and by study site. The proportions of participants experiencing these events will be calculated with corresponding exact confidence intervals for each group, and the difference between the groups will be compared using the Cochran-Mantel-Haenszel tests.

7.6.2 IUD successful insertion, failed IUD insertion, and incident adverse events during the insertion process

The Treated Population will be used for evaluating the incidence of successful IUD insertion and incident adverse events (e.g., perforation) occurred during the insertion process. The frequency and the percentage of women who experienced IUD placed successfully at the first attempt, at the second attempt, and incident adverse events occurred during the insertion process will be tabulated by treatment group and by study site. The proportions of participants experiencing these events will be calculated with corresponding exact confidence intervals for each group, and the difference between the groups will be compared using the Cochran-Mantel-Haenszel tests.

7.6.3 IUD expulsions, incident adverse events, and other events after a successful IUD insertion

The User Population will be used for analysis of IUD expulsions (complete and partial), incident adverse events, and other events. For each adverse effect (e.g., PID or uterine perforation), two measure units will be used in this analysis: 1) number of participants experiencing at least one adverse effect and 2) number of the AE reporting during the study. First, the proportions of participants experiencing the AE will be calculated using exact confidence intervals for each group and compared between groups using Fisher's exact tests or the Cochran-Mantel-Haenszel tests. Secondly, generalized linear models with GEE for repeated AE outcomes will be used to further explore the differences in the incidence of AEs between study groups.

Since participants with longer study duration will have more chance to experience adverse effects, the analysis will control for duration since insertion. Note that if the duration in study depends on adverse effects, then the drop out will be non-ignorable. Supporting stratified analyses by study duration or joint modeling of adverse effects and study duration will be considered as sensitivity analyses (Tsiatis and Davidian, 2004).

All expulsions (partial or complete) and accidental self-removals/dislodgements of the IUD will be examined in relationship to type of menstrual hygiene product used by the participant. Participants may use a variety of products over the course of the study. The mutually exclusive categories for analysis will include the following: Any cup use (exclusive cup use or cup use plus any other hygiene product), tampon use (no cup use but tampons used exclusively or tampon use plus other hygiene products), pad (no cup use, no tampon use, but pads used perhaps with some products other than tampons), other products (no cup use, no tampon use, no pad use). A sub-analysis will examine if the self-removal/dislodgement was known to occur during manipulation of the hygiene product. Chi-square tests and/or Fisher's exact tests will be used to examine these associations by IUD group. The proportions of participants with expulsions will be calculated using exact confidence intervals for each type of menstrual hygiene product in each group. Cochran-Mantel-Haenszel tests will be used as appropriate to compare IUD groups.

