The proportions of subjects experiencing any other side effects will be calculated with corresponding exact confidence intervals for each group, and compared the difference between groups by Fisher's exact tests or the Cochran-Mantel-Haenszel tests. Generalized linear model approaches for repeated occurrence side effect outcomes might be used to further assess the differences in the incidence of adverse events between study groups.

Overall satisfaction with the method will be summarized and compared between groups at the final study visit using two-sided Mantel-Haenszel chi-square tests. Similarly, the same statistical analysis methods will be used to describe ease of product insertion between groups. Changes in pain with and shortly after insertion from baseline will be described by the summary statistics (mean, median, inter-quartile, etc.) of visual analog scale measurements. The Mann-Whitney test or the analysis of variance method will be used to compare the changes in pain between groups.

For all secondary objectives, comparisons between groups will be made using two-sided 0.05 level significance tests, without adjustment for multiple comparisons.

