## 21.3 Risks and Benefits

## 21.3.1 Risks

Investigators will make efforts to minimise risks to participants. It is not expected that study procedures will expose human subjects to unreasonable risk. Pelvic examination and procedures may cause mild discomfort and/or vaginal bleeding or spotting. Women who learn they have a reproductive tract infection, in the course of the trial may experience worry, sadness or depression. Women who exhibit symptoms suggestive of clinical depression will be referred for counselling. Participation in clinical research includes the risks of loss of confidentiality and discomfort with the personal nature of questions when discussing sexual behaviours.

Participants at sites requiring partner notification in response to diagnosed STI infection could have problems in their relationships with their sexual partners. Participants also could have problems in their partner relationships associated with the use of a contraceptive method.

Site staff will make every effort to protect participant privacy while in the study. Although study sites make every effort to protect participant privacy and confidentiality, it is possible that participants' involvement in the study could become known to others, and that social harms may result.

The risks of using the ParaGard IUD are low, but do exist. IUD users are at risk of uterine perforation (including embedment) (1/1000), pregnancy, PID, or expulsion of the device (5% in the first year of use); all of these complications are rare. If perforation or IUD embedment occurs, it is possible that surgery will be needed to remove the product. Approximately 1% of IUD users experience PID in the three weeks after IUD insertion, then the risks decrease considerably thereafter. Approximately 50% of users experience increases in menstrual flow and number of days of bleeding. Approximately 20% experience intermenstrual spotting/bleeding, and about 35% experience painful menses. In addition, IUD insertion is uncomfortable for most women, although generally symptoms resolve within ten to fifteen minutes; symptoms are usually completely resolved within one day after insertion.

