1. INTRODUCTION

This is a multi-site, participant-blinded, randomized clinical trial. The study will randomize 1000 eligible participants in a 4:1 ratio to two different copper IUDs: 800 to Mona Lisa NT Cu380 Mini and 200 to ParaGard. Recruitment will be approximately 80% nulliparous and 20% parous women, and approximately 10% of women will be \geq 36 years old.

The total duration of the study is expected to be five years. The total duration for each participant is expected to be approximately 37 months. Each woman will attend a baseline visit, followed by visits at 6 weeks, 3 months, 6 months, 12 months, 24 months and 37 months, with telephones calls at 9, 18 and 30 months. Each subject will participate for up to 37 months (or less if the product is removed or expelled). Participants will use a home pregnancy test 17 days after Exit Visit procedures or any time she suspects that she may be pregnant, and report the results to their respective sites via telephone.

The analysis plan provides additional details regarding the planned statistical analysis of the study protocol (version 2.0, 09May17). Tables, figures and listings shells will be developed and included as an appendix to a future version of the plan.

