7.4.2 Statistical methods

The frequency and the percentage of women who complete the study or who leave the study for specific reasons, including loss to follow-up, will be tabulated. The percentage of discontinuation for each of the categories outlined above will be provided by study groups for the entire population. The duration of IUD exposure will be presented in summary tables using means, standard deviations, medians, interquartile ranges, minima and maxima by treatment group, site and overall.

For early discontinuation probabilities and comparative analyses, participants who complete full participation will be classified as censored. The product limit method (Kaplan and Meier, 1958) will be used to estimate 12-month, 24-month and 36-month cumulative probabilities (and associated 95% confidence intervals) for IUD discontinuation. A stratified logrank test by study site will be used to compare the discontinuation probabilities between the two groups of women, separately over the 12 and 36 months study periods. A non-stratified logrank test will be used if too few events (i.e., < 5) occur in one or more study sites.

As a supporting analysis, Cox's proportional hazards regression (Cox, 1972) will be used to assess differences in the risk of discontinuation between study groups, controlling for covariates. Suspected prognostic factors such as sociodemographic characteristics (i.e., age, education, relationship status), reproductive history (i.e., parity) and previous contraceptive experience (e.g., hormonal method use) will also be considered if they are significantly related to the outcome at the alpha=0.10 level in analyses of groups combined.

The assumption of proportional hazards will be assessed graphically and by testing for the significance of interaction terms between time (or functions of time) and other variables in the model if there is no time-dependent covariate in the model. If the proportional hazard assumption is violated, further data transformations or other methods will be considered. All interactions will be tested at the alpha=0.05 level.

To measure time to discontinuation due to a specific reason, such as menstrual pain, the same analysis strategy will be used. Competing reasons for removal will be considered independent and censored such as IUD expulsion, failed IUD insertion, uterine perforation, pregnancy, personal/non-medical reasons, and other medically-related reasons.

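### SAP 7.6.1 and 7.6.2 name only an unqualified Cochran-Mantel-Haenszel test; for very rare events such as perforation, its ordinary reading lets one ParaGard event reach p=0.0455

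*SAP*

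**What the plan says.** SAP 7.6.2 covers insertion success, insertion failure and "incident adverse events (e.g., perforation) occurred during the insertion process", in the Treated Population. For each arm it asks for exact limits: "The proportions of participants experiencing these events will be calculated with corresponding exact confidence intervals for each group". For the comparison between arms, 7.6.1 (exits before an insertion attempt) and 7.6.2 both say only that "the difference between the groups will be compared using the Cochran-Mantel-Haenszel tests". Neither section mentions an exact version, a continuity correction, a rule for small counts or a stratification factor.

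SAP 7.6.3, which covers events after a successful insertion and also cites uterine perforation as an example, is wider: proportions are "compared between groups using Fisher's exact tests or the Cochran-Mantel-Haenszel tests". Protocol 19.2.2 likewise allows "Fisher's exact tests or the Cochran-Mantel-Haenszel tests" for other side effects. Neither says when to use which.

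On size, SAP section 1 plans to "randomize 1000 eligible participants in a 4:1 ratio" (800 and 200). Protocol version 3.00 raises this to about 880 and 220. SAP section 6 makes all tests two-sided at 0.05 without multiplicity adjustment. Protocol 21.3.1 lists "uterine perforation (including embedment) (1/1000" among the risks of IUD use, and says that the levels of these complications are uncertain for the test product.

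**The concern.** If both arms share the protocol's rate, about one perforation is expected in the whole trial. A chi-square approximation has no basis at that count. With 4:1 allocation it fails in one direction: an event in the small arm is far from its expected 0.2, while an event in the large arm is close to its expected 0.8.

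A single chance perforation on the control device could therefore be reported as significantly more perforation with ParaGard. Uterine perforation is part of a named secondary endpoint, and the trial's rationale is that a smaller device may be better tolerated, so such a result would be noticed. The contrast with 7.6.3 suggests an oversight: a perforation at insertion has one test available, while a perforation found later may be tested exactly.

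**Working it through.** **Anchor.** The documents state no operating figure for this test. The nearest stated figure on the same 4:1 allocation is the 87% log-rank power for 12-month continuation (protocol 19.1: 70% against 80%, 5% lost). With HR = ln 0.8 / ln 0.7 = 0.626, 760 and 190 women after loss, and 760×0.2 + 190×0.3 = 209 events, Freedman's formula gives z = √(4×209) × (1−0.626)/(1+4×0.626) − 1.96 ≈ 1.13, or 87.1%. The stated figure reproduces.

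**Inputs.** 220 ParaGard and 880 Mini women (also 200 and 800); two-sided 0.05; perforation 1/1000 per protocol 21.3.1. Applying that rate to the Mini, and to insertion events alone, is an assumption, so a range of 0.05% to 0.5% is shown. Expected events at 1/1000: 1,100 × 0.001 = 1.1 (1.0 for 1,000 women).

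**One event.** CMH = (a − E)²/V, with E = n₁m/N and V = n₁n₀m(N−m)/[N²(N−1)]. For a = 1, m = 1: E = 220/1,100 = 0.2 and V = 0.2×0.8 = 0.16, so CMH = 0.8²/0.16 = 4.00 and p = 0.0455. The answer is the same at 200/800, and when stratified by parity or by site with exactly 4:1 in each stratum. Fisher's p is 0.20. One Mini event and no ParaGard event gives 0.2²/0.16 = 0.25, p = 0.617.

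**Three events, two on ParaGard.** CMH p = 0.043; Fisher p = 0.104.

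**Error with equal true rates.** Enumerating all pairs of binomial counts at 220/880, uncorrected and unstratified:

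| True rate, both arms | Expected events | CMH error | Fisher error |
|---|---|---|---|
| 0.05% | 0.55 | 6.9% | 0.4% |
| 0.1% | 1.1 | 9.0% | 0.9% |
| 0.2% | 2.2 | 8.6% | 1.6% |
| 0.3% | 3.3 | 7.0% | 1.8% |
| 0.5% | 5.5 | 4.7% | 1.9% |

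Every rejection in the table is against ParaGard. At 0.1%, most of the 9.0% is the single outcome of one ParaGard event and no Mini event: 220 × 0.001 × 0.999^1,099 = 7.3%. At 200/800 the CMH figures are 6.5%, 8.8%, 8.9% and 5.1% at 0.05%, 0.1%, 0.2% and 0.5%.

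**Where the excess ends.** Given the total number of events, the chance of a false CMH rejection is 20% for one event. For three it is about 3×0.2²×0.8 + 0.2³ = 10.4%, and for five about 5.8% (three or more on ParaGard). Two and four events give about 4.0% and 2.7%. The trouble lies in totals up to about five.

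**Stratified by site.** With one event the statistic is (1−s)/s, where s is ParaGard's share of the stratum holding the event. It exceeds 3.84 only if s ≤ 1/4.84 = 20.65%. A site with 12 ParaGard women of 62 gives 50/12 = 4.17, p = 0.041; 13 of 62 gives 49/13 = 3.77, p = 0.052. Simulation with 16 sites at 0.1% puts total error at 4.8% to 5.0%, all against ParaGard, and at about 10% given exactly one event.

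**The case against.** The SAP never says that the test is asymptotic, and an exact conditional CMH is not excluded. With a 0.5 continuity correction the one-event p-value is 0.453. Site stratification is a natural reading, since 7.1 and 7.4.2 stratify by site, and then two-sided error is close to nominal. The exact intervals would be tabulated beside any p-value: for 1/220 and 0/880 they are 0.01% to 2.5% and 0 to 0.42%, which overlap. The comparison is secondary and no decision rule hangs on it.

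Much of this stands, and it limits the point to a specification gap. It does not close the gap. The unqualified name ordinarily means the uncorrected chi-square version, 7.6.3 lists Fisher's test as a separate alternative, and 7.6.2 names no stratifier. The readings differ enough (p = 0.0455, 0.453 or 0.20 on the same data) that the choice should not be left until the data are seen.

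Three stronger inferences are tempting and should not be drawn.

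- **The lopsidedness is the test's fault.** CMH flags the Mini only from 16 events against none. Fisher needs 17 (p = 0.053 at 16, 0.032 at 17), and its rejections at 1/1000 also all point against ParaGard. The asymmetry comes from the 4:1 allocation.
- **Exact tests are needed up to about 25 events**, where the expected ParaGard count reaches 5. CMH error is already 4.7% at a 0.5% rate and 3.5% at 1%, so there is little or nothing to cure there and power for safety comparisons would be lost.
- **The log-rank tests in 7.4.2 share the fault.** That section says: "To measure time to discontinuation due to a specific reason, such as menstrual pain, the same analysis strategy will be used". A similar one-event result is plausible for rare removal reasons, but no error rate has been computed for it, so it is not part of this point.

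**Conclusion.** The point holds for very rare events only. On the ordinary reading of 7.6.1 and 7.6.2, one ParaGard perforation and none on the Mini is nominally significant, and the two-sided error at true rates of 0.05% to 0.3% is about 7% to 9% instead of 5%.

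This rests on four assumptions: an asymptotic test; no continuity correction; no stratification, or a ParaGard share of at most 20.65% in the stratum holding the event; and the same true rate in both arms. A reader might infer that any single ParaGard perforation must give p<0.05. The documents do not support that, because they fix neither the stratifier nor the version of the test; under site stratification about half of single ParaGard events would do so (10% of the 20% that fall on ParaGard).

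Commoner outcomes such as insertion success are not affected. Section 7.6.1 is affected only if its counts are this small, and the documents give no rates for those exits. The primary Pearl Index analysis is untouched.

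**What to change.** In SAP 7.6.1 and 7.6.2, name the stratification factor, or state that there is none. Say that sparse events, for example about 5 or fewer across both arms, are compared with Fisher's exact test or, if stratified, the exact conditional CMH test. In 7.6.3, make the exact test the rule at the same counts, so that the choice between two tests is not open once the data are known.

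The cost is a sentence or two in the SAP; SAS has the exact procedures. The statistical price is conservatism: Fisher's actual error is about 1% to 2% at rates of 0.1% to 0.5%, and lower still at 0.05%, so fewer rare-event differences will reach 0.05. With so few events, the exact interval for each arm, already planned, is the more useful summary.
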